5.2.8 Patients' quantitative experience with the use of distant video lessons

Descriptive statistics will be provided for the subject who watched all video lessons or not. A post-hoc analysis may be done to compare the two groups on the clinical outcomes such as HbA1c and insulin TDD.

5.2.9 General Considerations

- Missing Insulin or Glycemic data might be imputed, as described in section 5.2.10.
- Imputation might be used during questionnaire analysis if questionnaire pre-process tools contain an imputation routine.
- p-values less than 0.05 will be considered statistically significant. Multiple comparisons adjustments will be made when adequate.
- For each model above, in case the model fails to converge for discrete responses, the random subject effect may be dropped from the model and the average difference between time periods may be calculated across all subjects.
- Initially, two-way interaction will be included into the model. However, if the interaction is not significant (p-value ≥ 0.05), it will be removed from the final model.
- Main effect and interaction plots may be used to graphically show significant effects for each model.
- Residual plots for each model will be drawn and reviewed to ensure there are no systematic patterns. Transformation of response and/or explanatory variables will be investigated whenever modelling assumptions are not satisfied.

- For analysis on discrete responses, a modeling approach will be attempted first and in cases where there are insufficient occurrences for model convergence or a stable model, difference in proportions between categories will be provided and non-parametric testing may be used if modeling assumptions, with or without data transformation, are not satisfied.

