- 1) *Hemorrhages and hematomas.* Sometimes during an injection, the needle may damage blood vessels, causing hemorrhages or hematomas. Changes in needle length or other injection parameters do not seem to influence the rate of occurrence of bleeding or hematomas, although, according to some data, these complications may occur less frequently when short needles are used. Pressing on the injection site for 5-10 seconds should stop the bleeding [1].
- 2) *Leakage of the medication from the injection site.* This can occur due to the following reasons:
 - a) a one-time injection of a large insulin dose. In some cases, it would be preferable to divide large insulin doses into two doses and inject them one after another [1].
 - b) individual skin properties (dermal structure) and its age-related changes may be the cause of medication leakage following an injection [1].
- 3) *Pain.* Injections of insulin and GLP-1 receptor agonists do not usually cause pain, except for cases when the needle damages nerve ending fibers, which is a fairly rare event. However, some patients respond to injections in a rather sensitive way and describe their sensations as painful ones. Patient discomfort during injections was carefully studied and is attributed to three key factors: needle length, needle diameter and injection setting [1].

The benefit provided by this study is the demonstration of the fact that proper insulin injection technique used by patients is a prerequisite for achieving good glycemic control of diabetes, reducing the variability in the absorption of insulin preparations, and obtaining the optimal effect of their use [1]. Also, we expect that the proper technique of insulin injections will help to reduce the risks of injections: hemorrhages, hematomas cases and pain.

6. Objectives of the clinical trial and the hypotheses to be tested

The study aims at verifying the effect of teaching the optimal technique of insulin injection using the multimodal individual approach, supplemented with a personalized remote platform for the education of diabetic patients who are on insulin therapy, with regard to the clinical outcomes and essential skills necessary for managing diabetes.

This is a prospective study conducted in Russia, with a subsequent progress review after a 6-month follow-up to assess the correctness of insulin injection technique. The study design represents a “before” and “after” comparison, where the patient is left under

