10.2. Statistical analysis plan

For descriptive statistics and conclusive statistics, R 3.4.4 or more recent version and Rstudio will be used. The HbA1c and insulin total daily dose will be analyzed using linear models with mixed effects (with transformation or without it, whenever necessary) where

lipohypertrophy will be a fixed effect. Analyses will be done overall and per lipohypertrophy sub-group (with or without LH) whenever the sub-group effect is significant.. Generalized linear models with mixed effects will include logistic models for binomial responses or Poisson models for count responses.

Fixed effect models can be used when models with mixed effects cannot be employed. The effect of different covariates will be studied (including, but not limited to these), such as site, age, BMI, gender and diabetes type, as well as their interaction. The threshold to keep covariates in a model will be $p < 0.05$.

Non-parametric tests will be used if basic assumptions do not hold for the models.

McNemar's test will be used, when necessary, for contingency tables.

Statistical methods will be detailed in a Statistical Analysis Plan. Additional analyses may be performed and will be defined in the Statistical Analysis Plan.

11. Data management

All documents containing personal information of the study participants must be stored at the trial conduct site.

The data collected during the course of the study will be entered in the eCRF. The study participants will be identified by the study participant code which is generated by the eCRF. Patient confidentiality will be maintained throughout the study, including the publication of the study results. The principal investigator or sub-investigator will review and sign each form (eCRF, AE), the system will record the date when it was signed. The investigator's signature is the confirmation that clinical and laboratory data entered in the form are complete, accurate and veracious.

The data obtained and entered in the eCRF are the property of Becton, Dickinson and Company.

The study data, copies of the study materials and the medical documents will be provided to the Ethics Committee of the research center, the authorized bodies for internal audit should it be conducted, and on the audit demand. All data obtained in the course of the study will be stored confidentially for at least 3 years after the end of this trial.

12. Appendices to the clinical trial protocol

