5.2.6 Injection Techniques

If data permit, a logistic mixed effect models will be used evaluate the effect of personalized teaching of the optimal insulin injection technique in conjunction with the use of disposable BD Micro-Fine Plus 32G pen needles on the percentage of subject correctly alternating injection sites. In the model, subject will be a random effect, time period (baseline, 3 months or end of study) and lipohypertrophy will be fixed effects. Two-way interactions between fixed effects will be investigated. Only significant interactions will be included in the model. Models will be used to compute estimated mean, difference between baseline and end of study, and corresponding two-sided 95% CI for responses of interest. Additional information recorded in the CRFs will be summarized.

Similar approaches will be used for percentage of subject using needles repeatedly and subject injecting into lipohypertrophy areas.

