5.2.7 Change of lipohypertrophy

If data permit, a logistic mixed effect models will be used evaluate the effect of personalized teaching of the optimal insulin injection technique in conjunction with the use of disposable BD Micro-Fine Plus 32G pen needles on the percentage of subject with lipohypertrophy. In the model, subject will be a random effect, and time period (baseline, 3 months or end of study) will be fixed effects. Models will be used to compute estimated mean, difference between baseline and end of study, and corresponding two-sided 95% CI for responses of interest. Similar approaches will be used for lipohypertrophy size (length and width in mm) and localization (if applicable).

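### SAP 5.2.9 lets the subject effect be dropped from a non-converging discrete-response model and names no paired replacement, which makes the exploratory before-after comparisons inefficient

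*SAP*

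**What the plan says.** Protocol section 6 states that "The study design represents a “before” and “after” comparison", in a single arm. For injection technique, SAP 5.2.6 begins "If data permit, a logistic mixed effect models will be used" and specifies: "In the model, subject will be a random effect, time period (baseline, 3 months or end of study) and lipohypertrophy will be fixed effects". The same approach is planned for needle reuse and for injecting into lipohypertrophy. SAP 5.2.7 models the presence of lipohypertrophy in the same way, without the lipohypertrophy term: "subject will be a random effect, and time period (baseline, 3 months or end of study) will be fixed effects". Both sections promise the "difference between baseline and end of study, and corresponding two-sided 95% CI for responses of interest".

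SAP 5.2.9 then gives the fallback. "For each model above, in case the model fails to converge for discrete responses", it continues, "the random subject effect may be dropped from the model and the average difference between time periods may be calculated across all subjects". The last bullet of 5.2.9 covers much the same situation, too few events for a stable model. It offers a difference in proportions and an optional non-parametric test, but does not name the test or say that it is paired. Protocol 10.2 does name a paired test: "McNemar's test will be used, when necessary, for contingency tables". The SAP does not mention McNemar.

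**The concern.** In 5.2.6 and 5.2.7 the random subject effect is the only term that links a patient's three visits. Without it, and without GEE, clustered standard errors or a conditional model in its place, the logistic model treats baseline, month 3 and month 6 as if they came from different people. In a one-arm before-after study the pairing is what gives the comparison its precision.

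The promised 95% interval for the change is then wrong whenever the within-patient correlation is not zero. What is at stake is a fair reading of site rotation, needle reuse, injection into lipohypertrophy and lipohypertrophy presence. The first three belong to the protocol's additional objective. Two overlapping fallbacks with no order of use also leave the choice to be made after the data are seen.

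**Working it through.** **The plan's own figure.** The only sample size calculation is for HbA1c: a decrease of 0.4, SD of paired differences 1.2, one-sample t-test, alpha 0.05, power 80%. With a two-sided test this gives n = 73 and power 80.2%, so the stated 73 is reproduced and is not in question. It also supplies the n used below.

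**Assumptions.** The documents give no expected rates for rotation or needle reuse and no within-patient correlations. I use 73 complete pairs, 45% falling to 30%, and a binary correlation rho of 0.3, 0.5 and 0.7. For these margins the largest possible rho is (0.30 − 0.45×0.30)/√(0.2475×0.21) = 0.165/0.228 = 0.72, so 0.7 is close to the extreme.

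**Standard error of the change.**

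- Visits treated as independent: √[(p1q1 + p2q2)/n] = √[(0.2475 + 0.21)/73] = 0.0792, whatever rho is.
- Paired: √[(p1q1 + p2q2 − 2·rho·√(p1q1·p2q2))/n]. At rho 0.5 this is √[(0.4575 − 0.2280)/73] = 0.0561, and the ratio is 0.0792/0.0561 = 1.41.

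Power is computed from the multinomial distribution of the paired 2×2 table, two-sided 5%. Type I error uses 40% at both times.

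| rho | SE ratio, independent to paired | Power, independent | Power, McNemar asymptotic | Power, McNemar exact | Type I error, independent |
|---|---|---|---|---|---|
| 0.3 | 1.19 | 47% | 62% | 52% | 2.1% |
| 0.5 | 1.41 | 46% | 76% | 69% | 0.6% |
| 0.7 | 1.82 | 44% | 97% | 94% | 0.05% |

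At rho 0.2, exact McNemar gains nothing: 47% against 47% here, and 72% against 73% for a fall from 50% to 30%.

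**Near the boundary.** The correlation cannot exceed (min(p1,p2) − p1p2)/√(p1q1·p2q2), which limits the damage:

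| Change | Largest rho | Largest SE ratio |
|---|---|---|
| 45% to 5% | 0.25 | √(0.295/0.240) = 1.11 |
| 50% to 10% | 0.33 | √(0.340/0.240) = 1.19 |
| 30% to 5% | 0.35 | √(0.2575/0.1875) = 1.17 |
| 20% to 5% | 0.46 | √(0.2075/0.1275) = 1.28 |

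In the first three examples power exceeds 99% either way. For 20% to 5% at rho 0.3 it is 86% with visits treated as independent, 93% with asymptotic McNemar and 88% with exact McNemar.

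**Between-patient terms.** For a term that is constant over three visits, such as lipohypertrophy status in 5.2.6 if taken at baseline, the naive SE is 1/√(1 + 2·rho) of the correct one. That is 0.85, 0.75 and 0.67 at rho 0.2, 0.4 and 0.6, with type I error of about 10%, 14% and 19%.

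**The case against.** The strongest reply is that little depends on this rule. It is permissive, covers discrete responses only, and reaches models that are themselves conditional on the data and serve exploratory endpoints. HbA1c, total daily dose and glucose use linear mixed models. Hypoglycemia is only summarised in 5.2.5; the example tables with mixed models for it are labelled as coming from previous studies. The study has no acceptance criterion. All of this stands and limits the weight of the point.

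The average difference across all subjects could also mean a mean of within-patient differences, which would keep the pairing. That is possible, but no variance method is given, so the ambiguity remains. If non-convergence reflects almost no between-patient variance, dropping the term does little harm; the SAP does not restrict the rule to that case.

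A reader might infer three stronger things that the documents do not support:

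- That non-convergence is likely. The SAP foresees it, but no rates are given from which to judge. The one stated prevalence, about 50% lipohypertrophy at enrolment, is far from a boundary.
- That the large power losses belong to sparse outcomes. They arise at mid-range proportions with high correlation; near 0 or 1 the correlation is capped.
- That the plan has discarded paired testing. Protocol 10.2 still names McNemar, and the last bullet of 5.2.9 leaves room for it. What is missing is the link.

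**Conclusion.** The point holds as a gap in a fallback rule for exploratory outcomes. If the rule is used and visits are treated as independent, positive within-patient correlation makes the interval for the before-after change too wide and its test conservative. Under the assumed 45% to 30% and rho 0.3 to 0.7, the standard error is inflated by about 1.2 to 1.8. Near the boundary the inflation is at most about 1.1 to 1.3 in the examples checked, and at low correlation exact McNemar offers no gain.

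A reader might infer a risk of falsely claiming that training worked. For the change over time under positive correlation the error runs the other way; only between-patient terms become anti-conservative. The primary HbA1c conclusion is not affected. The sizes rest on assumed proportions and correlations, while the absence of a named paired fallback is plain from the text.

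**What to change.** Merge the two overlapping bullets in SAP 5.2.9 into one ordered rule:

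1. If the mixed logistic model does not converge, fit GEE clustered by patient with robust standard errors.
2. If that also fails, report the paired difference in proportions, end of study versus baseline, with a paired 95% CI and McNemar's test (mid-p or asymptotic when the number of discordant pairs allows, exact when they are sparse).
3. Do not use a model that treats a patient's visits as independent.

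This carries the McNemar test of protocol 10.2 into the SAP and ties it to non-convergence. It costs a sentence or two and standard R functions, with no new data and no change to the sample size.

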5.2.10 Approaches and Analyses for Missing Data and Other Data Issues

5.2.10.1 Glycaemic Data

Glycaemic data will only be included for analysis if 70% of the expected data is available, i.e. at least ten days over each 14 days period with at least one BGM measure.

Missing glycaemia data will be imputed using median value computed per period per subject when data is not available for a given day only if the data meet the availability of 70% of the expected data requirement.

5.2.10.2 Insulin Data

Insulin data will only be included for analysis if 70% of the expected data is available, i.e. at least ten days over each 14 days period with at least one basal Insulin dose record and at least ten days over each 14 days period with at least one bolus Insulin dose record. In case a patient did not use boluses, only basal requirements will have to be fulfilled. The pattern of basal and bolus doses can be different (e.g. a day with basal information can have no bolus information).

Missing basal and bolus insulin data will be imputed separately, before TDD computation, using median value computed per period per subject when data is not available for a given day only if the data meet the availability of 70% of the expected data criteria.

6 Summary of General Study Data

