7.2. Outcome measures for the clinical trial

- Reduction in glycated hemoglobin (HbA1c, in %);
- Insulin total daily dose (TDD);
- Incidence of hypoglycemia;
- Incidence of severe hypoglycemia (which require assistance by others);
- Change in Blood Glucose levels (measured by BGM)
- Correct alternation of injection sites;
- Cases of repeat needle use;
- Change of lipohypertrophy, its size (length and width in mm) and localization (if applicable);
- Cases of injection into lipohypertrophy areas (if applicable);
- Patients' quantitative experience with the use of distant video lessons.
- Quality of Life assessments (EQ-5D)

7.3. Inclusion/exclusion criteria.

The selection of patients will not be influenced by race, religion, socio-economic and other factors. Approximately 50% of the subjects to be enrolled will have lipohypertrophy areas and 50% of the subjects will not.

Inclusion criteria:

1. Type 1 or type 2 diabetes mellitus;
2. Patients (male and female) of 18 years of age and over;
3. At least 1 year of experience with insulin self-administration;
4. Use of insulin pen for insulin injections.
5. HbA1c > 7.5% measured at study entry or maximally 30 days prior to study entry..
6. BMI below 40 kg/m² at study entry.
7. Daily self-control of blood glucose level;
8. Access to the internet for watching video lessons.
9. Only outpatients are eligible for the study.
10. Availability of the patient's signed informed consent for inclusion in the study.

Exclusion criteria:

1. Pregnant women or women planning to become pregnant during the time of study, breastfeeding women;
2. Subjects using an insulin pump;
3. Those using treatment with a GLP-1 receptor agonists alone;
4. Subjects not fluent in Russian (reading and writing).
5. Patients at high risk for ketoacidosis and/or hyperglycemia.
6. Psychic, physical or any other reasons hampering patient participation in the study (based on the reasonable opinion of the physician-investigator).

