5.1 Derived Variables

5.1.1 Total Daily Dose

Total Daily Dose will be calculated as the sum of basal and bolus insulin dose per day from both diary data and CRF. The data from the two sources will be analyzed separately.

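### The diary insulin completeness rule waives the bolus count for patients without boluses but has no matching waiver for patients without basal insulin, so an eligible mealtime-only patient with a complete diary is lost from the diary-based TDD analysis

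*SAP*

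**What the plan says.** SAP 5.1.1 defines the variable: "Total Daily Dose will be calculated as the sum of basal and bolus insulin dose per day from both diary data and CRF". It adds: "The data from the two sources will be analyzed separately".

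SAP 5.2.10.2 sets the inclusion rule for insulin data at 70% of what is expected and spells this out as two counts, both of which must be met. The first is "at least ten days over each 14 days period with at least one basal Insulin dose record"; the second sets the same minimum number of days for bolus records. It then gives one waiver: "In case a patient did not use boluses, only basal requirements will have to be fulfilled". It allows basal and bolus records to fall on different days. Missing days are filled with the patient's median for the period, but "only if the data meet the availability of 70% of the expected data criteria".

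On regimen, the inclusion criteria (Protocol 7.3, repeated in SAP 2.2) ask for type 1 or type 2 diabetes, at least a year of self-injection, and "Use of insulin pen for insulin injections". None of them requires a basal insulin. Protocol 7.6 names intermediate- and long-acting insulins and short- and ultra short-acting insulins. Neither document mentions premixed insulin.

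**The concern.** A completeness rule should remove patients whose records are too thin to give a reliable dose. The waiver shows that the authors recognised that regimens differ, but it works in one direction only. A patient with no basal insulin has nothing to enter as basal, so the rule counts a correct diary as a missing one.

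TDD is a secondary endpoint (SAP 2.5.2). The model in SAP 5.2.3 includes day within period as a fixed effect, which only the daily diary can supply, because the CRF holds one day's dose before each visit (Protocol 7.5). If patients leave the diary analysis because of their regimen, it no longer describes the enrolled population. It would also cover different patients from the CRF-based analysis beside it, for a reason unrelated to data quality. Protocol section 10 stresses that the sample should represent Russian patients who inject insulin, and SAP section 4 makes all enrolled subjects the primary analysis population. An exclusion by regimen works against both.

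**Working it through.** **1. The threshold.** 0.70 × 14 = 9.8 days, so ten days is the smallest whole number that meets 70% (10/14 = 71.4%; 9/14 = 64.3%). The ten-day count agrees with the stated percentage.

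**2. The rule applied by regimen.** Assume a diary filled in on all 14 days of a period. A patient passes if basal days ≥ 10 and bolus days ≥ 10, with the bolus condition dropped if the patient uses no bolus.

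| Regimen and recording | Basal days | Bolus days | As written | With mirror waiver |
|---|---|---|---|---|
| Basal only | 14 | 0 | pass (waiver) | pass |
| Basal and bolus | 14 | 14 | pass | pass |
| Mealtime only | 0 | 14 | **fail** | pass |
| Premix recorded as bolus | 0 | 14 | **fail** | pass |
| Premix recorded as basal | 14 | 0 | pass (waiver) | pass |
| Premix split into both | 14 | 14 | pass | pass |

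Only patients whose records are all bolus change status. Imputation cannot rescue them: it starts only after the rule is met, and a patient with no basal record has no basal median to impute from.

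**3. Which analyses are affected.** The CRF dose is a single day before each visit, so a ten-of-14-day count can only work on diary data. The CRF-based TDD analysis and the HbA1c analysis (SAP 5.2.2) keep these patients.

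**4. The plan's sample size.** SAP 2.3 gives 73 subjects for HbA1c from a decrease of 0.4 and an SD of 1.2, so d = 0.4/1.2 = 0.333. An exact two-sided one-sample t-test at alpha 0.05 reaches 80% power at N = 73 (power 80.2%). The figure reproduces and is not affected by this point. No sample size is stated for TDD.

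**5. Possible size.** The documents give no regimen mix, so the share with no basal record is an assumption. Taking 73 evaluable patients:

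| Assumed share | Patients lost (at most) | Patients left | Smallest effect detectable with 80% power |
|---|---|---|---|
| 0% | 0 | 73 | 0.332 SD |
| 5% | 73 × 0.05 = 3.65, about 4 | 69 | 0.342 SD |
| 10% | 73 × 0.10 = 7.3, about 7 | 66 | 0.350 SD |
| 20% | 73 × 0.20 = 14.6, about 15 | 58 | 0.374 SD |

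The counts are upper limits for each share, because they assume that every such patient would otherwise have kept a qualifying diary. The last column uses a one-sample t-test on paired differences as a simple stand-in for the mixed model.

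**The case against.** The strongest reply is that the governing test is 70% of the *expected* data. The ten-day counts only illustrate it, and nobody expects basal records from a patient who uses no basal insulin. On that view a sensible analyst would apply the mirror waiver unprompted, and the omission is a drafting slip. This is plausible as to intent. But the section states the counts as the meaning of the 70%, and it writes out the exception for one component. An analyst who follows the text has no authority to add the other exception, and would have to decide with the data in hand.

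A second reply is that nothing in the documents says any mealtime-only patient is expected. That stands. Eligibility admits them but does not show that there are any.

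Three stronger readings are tempting, and the documents do not support them:

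- *Premixed insulin is excluded.* A premix patient fails only if the dose is recorded wholly as bolus. Recorded as basal or split, it passes. The fault is an undefined classification.
- *These patients drop out of the TDD endpoint altogether.* TDD is analysed twice, and only the diary version applies the rule.
- *One thin period removes the patient from all periods.* The wording about each 14-day period could be read that way, but imputation in the same section works per period and per subject, and the model in SAP 5.2.3 (period fixed, subject random) tolerates a missing period. The same phrase appears for glucose in SAP 5.2.10.1, so it is not part of the waiver gap. It merits a clarifying clause and adds no weight to this point.

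**Conclusion.** Wrong as written, within a narrow scope. The rule in SAP 5.2.10.2 excludes an eligible patient with a complete diary because of the regimen used, not because of data quality, and nothing else in the section reverses that.

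The effect is confined to the diary-based analysis of one secondary endpoint. The main consequence is that the patients analysed are selected by regimen. The loss of precision is modest: even with 10% lost, the detectable effect moves only from 0.332 to 0.350 SD.

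The number affected cannot be determined from the documents and may be small or zero. The range of about 4 to 15 of 73 rests entirely on assumed shares of 5% to 20% with no basal record. For premixed insulin, the conclusion depends on a recording convention that the documents leave open.

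**What to change.** Amend SAP 5.2.10.2, before the data are analysed, to say that:

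1. the ten-of-14-day requirement applies only to the insulin component or components the patient uses in that period, so that a patient without basal insulin need meet only the bolus count;
2. premixed doses are classified by a stated convention, so that each dose counts once towards TDD and counts towards the completeness rule;
3. the rule applies to diary data only and is assessed period by period, so that a period that fails does not remove the others.

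The SAP should also say how use of a component is established, so that a patient who does not use basal insulin can be told from one who did not record it. The existing waiver already needs this for boluses. The basal and bolus doses captured in the eCRF for the day before each visit offer an independent check.

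The cost is a few sentences and one derived variable. The documents describe only basal and bolus capture, so the sponsor should confirm that the diary or eCRF identifies premixed insulin. No change to treatment or visits is involved.
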